7.1.1 Participant identification

Eligible potential transplant recipient participants will be identified by the PIs in each centre from their centre's heart transplant waiting list. All eligible patients will then be sent a letter by their transplant centre advertising the study and containing the participant information sheet. Access to personally identifiable information will be performed by the PI or delegated individual in each centre, who is a member of the transplant care team. The letters will be addressed and sent by the PI or delegated individual(s). This process will not be contracted to a third-party mailing service.

Eligible potential donor cardiac allografts will be identified by the transplant coordinator or designated person in the recipient centre at the time of the offer of a donor cardiac allograft to the UK NORS.

The eligibility of potential transplant recipient participants will be confirmed by the designated person taking informed consent in their UK cardiothoracic transplant centre, at the time when the informed consent discussion takes place.

The eligibility of potential donor cardiac allografts will be confirmed by a member of the retrieving UK NORS team.

7.1.2 Screening

Eligibility screening will require the potential transplant recipient participant's transplant clinician to review their medical notes and ensure that they meet the eligibility requirement prior to commencing the informed consent discussion. There will be no extra investigations, procedures or questionnaires required to confirm eligibility. The process and outcome of eligibility screening should be recorded in the screening and eligibility log.

Potential transplant recipient participants may become ineligible or eligible during the study, as their status on the Heart Transplant waiting list is subject to change, depending on their clinical circumstances. Final confirmation of eligibility and informed consent will occur just prior to their receipt of a transplant.

7.1.3 Payment

No payments will be made to potential participants, confirmed participants, organ donors or their families for their involvement in this study. It is not anticipated that participants or donors will incur any extra costs as a result of taking part in this study.

7.2 Consent

7.2.1 Potential Transplant Recipient Participants

For potential transplant recipient participants, the informed consent process will take place over a period leading up to their receipt of a cardiac transplant in the UK. See the Informed Consent Process Flow Diagram (Figure 2, p. 13) for an overview.

The process will begin with the receipt of an invitation letter and participant information sheet in the post. The letters will be sent by the direct care teams in each centre. PIs or delegated individuals who are members of the transplant care team in each of the individual centres will access the names and addresses (personal identifiable information) of all patients on the waiting list for a heart transplant at their institution for this purpose.

The next step in the process will take place during the next in-hospital contact between the potential recipient participant and their transplant team. This is most likely to be their next follow-up appointment in clinic at their transplant centre but may occasionally be when they are called to the hospital to receive their transplant or have an inpatient admission at their transplant centre for another reason. The preferred option is for this contact to take place in the clinic.

The Chief Investigator (CI) delegates the responsibility to take informed consent to the Principal Investigator (PI) in each centre. The PI in each centre may delegate responsibility to take informed consent to clinicians or specialist nurses in each transplant centre, once they have received training during their location centre induction, provided evidence of GCP training and signed the Delegation and Training Logs in their local centre.

The approach to participate in an informed consent discussion should be made at an appropriate time and in an appropriate setting, as decided by the person taking consent. The informed consent discussion should start by taking consent to participate in the discussion about the study. Implied consent through the continuation of the discussion will be acceptable for this. The potential participant should be offered the opportunity to have other individuals present for support if they wish. The potential participant should also be offered the opportunity to take part in the discussion at an alternative time or in an alternative setting that is more convenient to them. The potential participant should be provided with the participant information sheet, given a verbal summary by the person taking consent and then afforded time to read the participant information sheet in full. The person taking consent should answer any questions that the potential participant or their family or other representatives (where present) have. The potential participant should then be offered a period of reflection prior to taking written evidence of informed consent. Ideally, this should not take place until the next in-hospital contact, to allow the potential participant to reflect at home and discuss participation with their family. The next in-hospital contact may be their next clinic appointment, an in-patient admission or when they are called to the hospital to receive their transplant. Where requested by the potential participant, written evidence of informed consent may be taken in the same in-hospital episode as the first approach, after a period of reflection. Where the potential participant declines to consent, this should be recorded, and no further approaches should be made unless expressly requested by the potential participant. The person approaching potential

[figure not shown]

participants for an informed consent discussion must always check their local centre pack to ensure that the patient has not been approached before and declined to consent. Any potential participant who declines to consent should be informed that they do not need to give a reason for declining. Where a reason is given, this should be recorded.

Where the approach is made when the potential participant is called to receive their transplant, the member of the direct care team who will be taking consent will ensure the approach is made at an appropriate time, in an appropriate setting and that adequate time is left for the potential participant to read the participant information sheet, reflect and ask questions before taking written evidence of informed consent. Where the approach is made during hospital admission for another reason, the approach should not be made until the potential participant is sufficiently recovered to take a full and active part in the informed consent discussion. This will be judged by the potential participant's direct care team. The potential participant should be offered the opportunity to decline to take part in the discussion at that time and be offered an alternative time.

All potential participants, regardless of when they provided written evidence of informed consent, must have their ongoing consent confirmed just before their receipt of a transplant. Verbal confirmation of consent, documented on the consent form, by an appropriate person listed in the Delegation Log, is acceptable for this purpose.

Figure 4: Steps in the Informed Consent Process

7.2.2 Potential Donor Participants:

Potential donor participants' families are approached by the specialist nurse in organ donation (SNOD) to take part in an informed consent discussion regarding organ donation. There will be no changes to this process as a result of this study. This discussion includes a question on whether the donor family consent for the organs to participate in research. In order for a donor heart to be eligible to be included in this study the donor family must have given consent for the organs to participate in research. This consent will be checked at randomisation against the eligibility criteria.

During the development of this Protocol, the consent process has been extensively discussed within NHS Blood and Transplant's Research and Quality Assurance teams, who are responsible for maintaining regulatory compliance and act as advocates for our donors and their families. This concluded that specific donor consent for participation in this study is not required. The primary reason for this is that perfusion fluid is not discussed with a donor family and organ perfusion with any licensed product is an integral part of consent for organ donation.

Other reasons include:

i. Donor families often feel burdened by the amount of information provided as part of the organ donation consent process. Asking for specific consent is not only unnecessary but may also be detrimental to donor families at a time of grief.

- ii. The intervention being applied by random allocation in this study will not have an effect on the donor, who is deceased, but may have an effect on the recipient, who therefore must provide informed consent.
- iii. No relevant material is being removed as part of the study and therefore consent is not required under the Human Tissue Act (2004).
- iv. No additional data is being collected on the donor. Any donor-related data required by the study will be routinely collected by NHSBT and supplied to the research team in a secure and anonymised form.

7.2.3 Translation:

Where English is not the participant's first language, or if a verbal translation is requested, this will be via a hospital interpreter, where available. When a hospital interpreter is not available in person, hospital-provided telephone translation services are acceptable. Written material will be translated on request to the trial manager, who will contract an NHS-approved translation service for this purpose. As all centres are in England or Scotland, written material will not routinely be provided in Welsh, but can be requested in Welsh by any potential participant, whereupon the trial manager will arrange translation by an NHS-approved translation service, as above.

7.2.4 Participant Withdrawal:

Recipient participants are free to withdraw at any time on request to the CI or their local PI. Where given, a reason for withdrawal from the study will be recorded. Discontinuation of the trial treatment or withdrawal of consent by the recipient for any reason should be communicated to the Sponsor as soon as possible by email.

Where transplant recipient participants withdraw consent prior to organ retrieval, the donor heart will not be randomised and no additional data, beyond the minimum dataset of age, sex, ethnicity, approach to consent and outcome of consent discussion, will be collected on the recipient. Data on donors whose corresponding recipient withdraws consent, or did not provide consent, will not be requested from NHSBT. Where transplant recipient participants withdraw consent after organ retrieval, data collected up to that point will be included in the data reported for the trial. No outcome data will be collected from that recipient but data from the NHSBT Transplant registry may still be accessed unless the withdrawing participant expressly denies this. They should be offered the opportunity to deny this consent, and the outcome should be recorded on the withdrawal of consent form. Furthermore, data on the donor of a participant who withdraws consent after organ retrieval may be requested from NHSBT.

Please note, for the definition of withdrawal of consent before and after organ donation/retrieval, the point of organ donation/retrieval will be considered the point at which the WHO pre-operative briefing commences in the operating theatre. This time point has been chosen because the entire surgical retrieval team must know whether there will be a randomisation process during the retrieval operation and prepare accordingly. It would not be safe to change the plan after this time. Where consent is withdrawn prior to this point, the retrieval will still proceed but no trial treatment will be applied, and the heart will be preserved in whichever solution the surgeon prefers; this would normally be STH in accordance with current NORS Protocols.

7.3 The randomisation scheme

Randomisation of hearts will occur after consent of the recipient has been secured and after the heart has been deemed acceptable by the medical team. Permuted blocks will be used to randomise each heart to one of the two treatments while ensuring a 1:1 overall allocation ratio. The randomisation will be performed using the secure online platform SealedEnvelope (Sealed Envelope Ltd. 2022. Simple randomisation service. [Online] Available from: https://www.sealedenvelope.com/simple-randomiser/v1/ [Accessed 25 May 2023]). Once consent to participate in the study has been confirmed on the part of the recipient and the suitability of the heart for transplant has been confirmed, the PI, or delegated individual at the transplant recipient centre, will access SealedEnvelope, via a secure and traceable login and generate a random allocation, which will be sent via email to the randomiser and the trial manager. Please note that the randomisation procedure should not be conducted until the intention to proceed with cardiac donation to the named recipient has been confirmed. This should be after the retrieval operation has begun and the retrieval team have assessed the heart in situ and confirmed its suitability for transplant. It is routine for the recipient transplant coordinator to be contacted via telephone during the retrieval operation once suitability to transplant has been confirmed and therefore the randomisation should occur at this stage. This will not delay the retrieval operation. The retrieval team must include the instructions for delivery of both solutions at the WHO pre-operative briefing. It will be the randomiser's responsibility to inform the NORS team of the outcome of the randomisation in a timely manner, via telephone.

Each NORS team will maintain both treatments, and the equipment required to use either treatment, at all times and take both treatments with them to the retrieval centre. Once they have been informed of the treatment allocation, they will prepare and administer the treatment in accordance with the methods set out in this Protocol. Refer to the trial's 'Registration and Randomisation Guidelines for Sites' for more information.

7.4 Blinding

The trial is single (participant) blind. Care providers involved in the transplant process cannot be blinded due to the different administration regimes for each treatment. Anyone who is not directly involved in the organ retrieval or transplant operations should not be informed of or seek to discover the treatment allocation. It will be the responsibility of the local PI in each centre to minimise the number of individuals who are aware of the treatment allocation.

Ideally, the outcome assessor who inputs clinical outcome data to the database should be blind to the treatment allocation. However, this is unlikely to be practically possible, due to the limited number of people involved in the transplant process. In order to assess the feasibility of keeping outcome assessors blind, each time an outcome assessor inputs data to the database they will be asked to record whether it would have been possible for them to remain blinded (i.e., did they already know the treatment allocation through previous involvement in the transplant). It is the responsibility of the local PI to ensure that appropriate individual(s) are in place to record clinical outcome data.

Local induction packs and training will stress the importance of the treatment allocation remaining unknown to anyone outside of the teams directly involved in performing the organ retrieval and transplant implantation procedures. However, it will be necessary to record the preservative solution and its method and volume of administration on the operation note. The CI acknowledges that any healthcare individual with access to the patient's operation notes and medical records may have access to this. However, doing so in order to discover the treatment allocation, except under the circumstances outlined below in Emergency Unblinding, would be in breach of the General Data Protection Regulation (GDPR) and the UK Data Protection Act (2018).

F-CUSToS Protocol

Version Number 2.0; Dated 30 January 2025

Access to medical records is monitored within all NHS organisations and should be reviewed by the PI where there is any concern of inappropriate access to identify the treatment allocation.

Donor family and transplant recipients should not be informed of their treatment allocation, except under the circumstances outlined below for Emergency Unblinding.

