4 TRIAL DESIGN

This is a feasibility study of a single-blind, national, multi-centre, randomised controlled trial. The purpose of the trial is to assess the methodology and feasibility of conducting an appropriately powered efficacy randomised controlled trial comparing Custodiol-HTK with St Thomas' solution for donor cardiac allograft preservation during cardiac transplantation. The design, therefore, replicates a larger efficacy randomised controlled trial, differing only in its primary outcome, as described above.

The trial will be conducted at all six UK adult cardiothoracic transplant centres. Donor hearts included in the study will be randomly allocated on a 1:1 basis to receive either Custodiol-HTK or St Thomas' solution as cardioplegia and preservative solution during the organ retrieval process. Participants (recipients of donor cardiac allografts that have received one of the above treatments as part of the random allocation process) will be blinded to their treatment allocation. It is not possible to blind the healthcare staff involved in the transplant process as the solutions have different volumes and methods of administration and are different colours. Healthcare staff who look after the recipient but were not directly involved in the transplant retrieval or implant procedures should not be informed of the treatment allocation.

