- iii. Body surface area calculated using the DuBois and DuBois formula: Body Surface Area= 0.007184 x (Height(m) $^{0.725}$) x (Weight(kg) $^{0.425}$).
- iv. Mean Arterial Pressure (mmHg) on invasive intra-arterial blood-pressure monitoring at the time of Swan-Ganz measurements.
- v. Central Venous Pressure (mmHg) on invasive central venous pressure monitoring at the time of Swan-Ganz measurements.

As this is an exploratory outcome measure, with the intent to assess its utility based on real-world data, this will be assessed based on the above data being recorded on the intensive care electronic health record system. The measurements will be taken and recorded by the healthcare professional(s) looking after the participant. Where the outcome assessor transferring this data from the healthcare record to the trial database cannot find a measurement within the stipulated timeframe, this will be treated as missing data.

PGD will be determined based on the ISHLT consensus statement 2014 (2) and graded accordingly. PGD is defined as occurring within 24 hours, therefore all measurements included below must be taken within the first 24 hours after admission to ICU post-transplant procedure. Its definition requires the following variables to be recorded on the database:

F-CUSToS Protocol

Version Number 2.0; Dated 30 January 2025

- Ejection fraction on echocardiogram; where multiple measurements are taken the lowest estimate of ejection fraction recorded will be inputted to the database.
- ii. Haemodynamic variables taken at the time of a Swan Ganz measurement*:
 - (i) Central Venous Pressure (mmHg)
 - (ii) Pulmonary capillary wedge pressure (mmHg)
 - (iii)Cardiac Output (L/min)
 - (iv) Cardiac Index (L/min/m2)
 - (v) Mean Arterial Pressure (mmHg)
 - (vi)Transpulmonary gradient (mmHg)
 - (vii) Pulmonary artery systolic pressure (mmHg)
- iii. Vasoactive Inotrope Score (VIS), where VIS = dopamine [μ g kg⁻¹ min⁻¹] + dobutamine [μ g kg⁻¹min⁻¹] + 100×adrenaline [μ g kg⁻¹ min⁻¹] + 50×levosimendan [μ g kg⁻¹ min⁻¹] + 10×milrinone [μ g kg⁻¹ min⁻¹] + 10 000×vasopressin [units kg⁻¹ min⁻¹] + 100×noradrenaline dose [μ g kg⁻¹ min⁻¹].
- iv. Presence/absence of an intra-aortic balloon pump (IABP).
- v. Presence/absence of mechanical circulatory support (ECMO/LVAD/RVAD/BiVAD).

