*Where multiple Swan Ganz measurements are taken within the first 24 hours after transplant, the set of variables taken at the same time as the highest inotrope score should be uploaded to the CRF. Where there are multiple Swan Ganz measurements with the same inotrope score the set of variables with the lowest cardiac output should be uploaded to the CRF.

The following echocardiographic parameters from trans-oesophageal echo immediately after transplant implantation will be recorded in the initial outcome data collection CRF:

- i. Left Ventricular ejection fraction (% estimated by Simpson's biplane method)
- ii. Left ventricular maximal posterior wall thickness (in mm)
- iii. Maximal septal wall thickness (in mm)
- iv. Left ventricular function (good, moderate, poor or very poor)
- v. Right ventricular function (good, moderate, poor or very poor)
- vi. The presence/absence of any regional wall motion abnormalities as determined by the TOE operator

30-day outcome data collection: The delegated individual(s) in the recipient centre should upload the 30-day mortality, postoperative complication, length of initial ICU stay, and length of initial hospital stay data, on the 31st day after the transplant procedure. This should be conducted in accordance with the blinding instructions laid out in section 7.4 of this Protocol. The variables will be entered into the CRF as follows:

- i. 30-day mortality: alive/dead
- ii. Post-operative complications:
 - (i) Dysrhythmias (any within 30 days):
 - 1. Atrial fibrillation yes/no
 - 2. Ventricular tachycardia yes/no
 - 3. Ventricular fibrillation yes/no
 - 4. Other rhythm abnormality yes/no (specify)
 - (ii) Myocardial Infarction within 30 days (defined according to ESC definitions of myocardial infarction post-cardiac surgery): yes/no

- (iii)Stroke within 30 days (defined by radiological evidence of ischaemia/haemorrhage and clinical symptoms of stroke): yes/no
- (iv)Transplant rejection within 30 days (defined by the clinical team and confirmed on histopathology of biopsy material or post-mortem): yes/no
- (v) Infection within 30 days (from any source requiring antibiotic therapy): yes/no (specify suspected source)
- (vi) Venous thromboembolism within 30 days (defined by radiological evidence and need for treatment): yes/no (specify PE/DVT)
- (vii) 30-day re-admission to any UK hospital: yes/no
- (viii)Hyponatraemia within 24 hours of transplant (Na<125mEq/L on serum sample, not blood gas analysis): yes/no

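### Section 7.4 exempts the whole implant team from blinding, but its reasons are not shown to reach the TOE operator who makes the echo readings for secondary endpoint vi, and the blinding question goes only to the person entering data

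*Protocol*

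**What the plan says.** The trial is described as participant-blind. On staff, section 7.4 states: "Care providers involved in the transplant process cannot be blinded due to the different administration regimes for each treatment". Section 4 makes the same claim, "It is not possible to blind the healthcare staff involved in the transplant process", and gives three grounds: the solutions differ in volume, in how they are given and in colour.

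The line is drawn around both operations. Under section 7.4 the training material is to stress that the allocation stays unknown to "anyone outside of the teams directly involved in performing the organ retrieval and transplant implantation procedures". Section 7.5 treats a clinician who took no direct part in either operation as one who does not already know the allocation.

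Section 7.3 places administration with the National Organ Retrieval Service team at the donor site: "Once they have been informed of the treatment allocation, they will prepare and administer the treatment".

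The TOE is listed in Appendix 2 as an intra-operative procedure at implantation. Section 7.7 takes from it LVEF, two wall thicknesses, left and right ventricular function on a four-level scale from good to very poor, and "The presence/absence of any regional wall motion abnormalities as determined by the TOE operator". These are secondary endpoint vi in section 3.3.2.

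On assessors, section 7.4 says: "Ideally, the outcome assessor who inputs clinical outcome data to the database should be blind to the treatment allocation". It then concedes that this is unlikely to be achievable, and asks those entering data to record whether they could have stayed blind. Section 7.9 says the answers will be used to judge whether outcome assessors can be blinded in the larger trial.

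**The concern.** Blinding protects a reading only if it covers the person who makes it. For endpoint vi that person is the TOE operator. Nothing in the protocol says whether the operator should be unaware of the solution, and the line drawn in sections 4, 7.4 and 7.5 leaves the operator inside the exempt group, or at least not separated from it. Blinding whoever later copies the grade into the database cannot remove an expectation already built into it.

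Two things are at stake. First, section 10.3.3 names echo parameters and LVEF as examples of between-arm comparisons, and some of these readings are subjective. The background section expects Custodiol-HTK to do better, although the formal hypotheses in section 3.2 claim only a difference. Second, testing whether assessors can be blinded is a stated aim of this study, and section 4 says the design replicates the efficacy trial apart from its primary outcome. With the question put only at data entry, the study will end without knowing whether echo readers can be kept unaware.

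**Working it through.** The protocol gives no figure on this point, so the check is mainly a comparison of passages.

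**Step 1: which staff do the stated reasons reach?**

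| Reason or route | Source | Who it reaches |
|---|---|---|
| Different administration regimes | 7.4; administration by the retrieval team in 7.3 and 8.6 | Retrieval team at the donor hospital |
| Different volumes and colours | 4 | Retrieval team; anyone who sees the fluid |
| Inner storage bag holds Custodiol-HTK in one arm, saline in the other | 8.6.1, 8.6.2 | Staff who open the bag and handle the heart |
| Recipient surgeon may request a change to the St Thomas' doses | 8.6.2 | Implanting surgeon |
| Allocation generated at the recipient centre | 7.3 | Randomiser, who telephones the retrieval team |
| Solution, method and volume entered in the operation note | 7.4 | Its author, and anyone who opens it |

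No row is specific to the TOE operator. The operator might learn the solution by being in the same theatre, but the protocol neither says so nor gives a reason why it must happen.

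**Step 2: who makes the endpoint vi readings?** Section 7.7 names the TOE operator for regional wall motion. The four-level ventricular grades, LVEF and the wall thicknesses come from the same examination. LVEF has a specified method (Simpson's biplane). The ventricular grades and wall motion are the more subjective items.

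**Step 3: whom do assessor blinding and its question cover?** In section 7.4 the assessor is the person who inputs data. Section 7.7, on CPOi, describes the same role as copying: "Where the outcome assessor transferring this data from the healthcare record to the trial database cannot find a measurement". Section 7.9 puts the blinding question to those who record data in the CRFs. No item asks about the person who graded the echo.

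**Step 4: what could an aware reading do?** This is an illustration. The SD and the shift are assumptions; neither is in the protocol. Take LVEF with no true difference, a shift d between arms caused by knowledge of the allocation, n per arm and a two-sided 5% test of means. With equal variances and arm sizes, the Welch test is well approximated by the noncentral t distribution with 2n − 2 degrees of freedom and noncentrality d / (SD × √(2/n)).

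For n = 25 (50 patients split 1:1), SD = 10 and d = 3: 3 / (10 × √0.08) = 3 / 2.828 = 1.06. With critical value 2.011 on 48 degrees of freedom, the rejection rate is 18.0%, against 5% with no shift.

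| SD (25 per arm) | d = 2 | d = 3 | d = 5 |
|---|---|---|---|
| 8 | 14% | 25% | 58% |
| 10 | 11% | 18% | 41% |
| 12 | 9% | 14% | 30% |

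At 200 per arm (the 400 patients of the planned main trial) and SD 10, the noncentrality is d / (10 × √0.01) = d / 1, so d = 2 gives about 51% and d = 3 about 85%. A larger sample makes a fixed reading bias more likely to be declared significant.

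**The case against.** The strongest reply is that the allocation is known at the implanting centre by several routes, as Step 1 shows. A reader might infer that the only reason given for exempting theatre staff applies to the retrieval team alone. That fits the single sentence in section 7.4 but not the protocol as a whole, since section 4 adds volume and colour and the storage fluid differs by arm on arrival. The exemption is therefore reasonable for the implanting surgeon and for those who handle the bag.

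A reader might also infer that only the person entering data is meant to be blind. That is not so. Participants, donor families and staff outside both operations are to be kept unaware, and blinding of the data-entry person is only an ideal.

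A further tempting step is to carry the bias over to PGD, through support started in theatre. The documents do not support it: section 7.7 takes the PGD measurements in the 24 hours after ICU admission, the intra-operative TOE is a separate data item, and ICU staff not involved in either operation are already to be kept unaware.

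It can also be said that section 7.4 already asks the local PI to keep to a minimum the number of people who know the allocation. That duty could cover the TOE operator, but the training sentence draws the line around the whole implant team, so a site following its training would have no reason to apply it there. Finally, blinding inside one theatre will sometimes fail. That is true, and it is the reason to record awareness.

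**Conclusion.** The point holds for the TOE operator and secondary endpoint vi. The protocol exempts the whole implant team for reasons not shown to reach that operator, and puts its blinding-feasibility question to the wrong person for the echo readings. That second part rests on the text alone and needs no assumption about bias.

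The size is modest. The primary endpoint is a feasibility proportion and is untouched. No effect on PGD is shown. The false-positive rates in Step 4 depend entirely on assumed SDs and shifts and are run on LVEF, the item with a specified quantitative method. They show how sensitive the comparison would be, and are no evidence that bias will occur. The point is worth acting on because the gap would pass into the main trial and the remedy is cheap.

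**What to change.** 1. In sections 4 and 7.4, and in the induction-pack sentence, limit those who may know the allocation to the retrieval team, the randomiser, the implanting surgeon and staff who handle the storage bag.
2. State that the TOE operator is not to be told the solution where practicable, with the section 7.5 unblinding route kept open.
3. Add one yes/no item to the TOE page of the initial outcome CRF: did the person grading the echo know the allocation at the time? Report endpoint vi by reader awareness, and use the answers under section 7.9 to judge whether echo readers can be blinded in the main trial.

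The cost is a few sentences in the protocol and training pack and one tick-box, with no extra staff or procedure. The downside is that it relies on theatre discipline and will not always hold, which the CRF item will record.
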